5.5.3 Additional Safety Assessments

5.5.3.1 Clinical laboratory evaluations

The protocol-required laboratory parameters collected within UP0152 are given in [Table 11](#). All non-protocol-required laboratory parameters will not be presented in any tabulated summaries but will be listed.

Table 11 Protocol-required Laboratory Assessments

Laboratory Assessment	Parameters
Hematology	Platelet count
	Red blood cell count
	Hemoglobin
	Hematocrit
	Red blood cell indices – Mean corpuscular volume, Mean corpuscular hemoglobin, % reticulocytes.
	*White blood cell counts with differentials – Neutrophils, Lymphocytes, Monocytes, Eosinophils, Basophils
Clinical Chemistry	Blood urea nitrogen
	Potassium
	Aspartate Aminotransferase/Serum Glutamic-Oxaloacetic Transaminase
	Total and direct bilirubin
	Creatinine
	Sodium
	Alanine Aminotransferase/Serum Glutamic-Pyruvic Transaminase
	Total Protein
	Glucose (fasted)
	Calcium
Routine Urea (Urinalysis)	Alkaline Phosphatase
	Specific gravity
	pH, glucose, protein, blood, ketones, bilirubin, urobilinogen, nitrite, leukocyte esterase by dipstick
Microscopic examination (if blood or protein is abnormal)	

Laboratory Assessment	Parameters
	Renal biomarker analysis (Cystatin C)
Other screening tests	Follicle-stimulating hormone (FSH) and estradiol (as needed in women of non-childbearing potential only)
	Urine drug screen (to include at minimum: amphetamines, barbiturates, cocaine, opiates, cannabinoids, methadone, and benzodiazepines)
	Serum and urine human chorionic gonadotropin (hCG) pregnancy test (as needed for women of childbearing potential)
	Serology (HIV antibody, HBsAg and hepatitis C virus antibody)

*White blood cell count parameters will be presented by absolute values only.

5.5.3.1.1 Laboratory values over time

Laboratory variables and changes from Baseline will be summarized using descriptive statistics by time point and sequence. A by-participant listing will be provided for the SS.

Measurements that are below the limit of quantification (BLQ) or above the limit of quantification (ALQ) will be presented as BLQ or ALQ in the listings. For the purpose of calculating change from Baseline or for descriptive statistics, BLQ values will be imputed with half of the lower limit of quantification (LLoQ) and ALQ values will be imputed to the upper quantification limit.

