9.2.4 Secondary safety endpoints analysis

Secondary safety endpoints in this study are the occurrence of TEAEs, treatment-emergent SAEs, and the occurrence of TEAEs leading to withdrawal from the study.

Unless stated otherwise, all safety analyses will be performed on the SS.

All AEs will be coded using the most recent Medical Dictionary for Regulatory Activities (MedDRA®) and characterized as pre-treatment and treatment-emergent according to the intake of the IMP.

The occurrence and incidence of TEAEs will be summarized by MedDRA system organ class and preferred term and by treatment group. The occurrence and incidence of TEAEs will also be summarized by maximum event intensity and by relationship to the study medication. Adverse events will be categorized by severity (mild/moderate/severe). Adverse events leading to discontinuation and SAEs will also be summarized by treatment group. All AEs will be listed and will include actions taken for each AE, the time of onset of the AE after dosing, and the duration of each AE.

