9.2.4.1 Exploratory safety endpoints analysis

Laboratory variables and changes from Baseline (Day -1, or Day 1 before first treatment) will be summarized by time point and will be presented by treatment group. For categorized values according to the reference range, shift tables from Baseline to each post-Baseline time point will be presented for selected variables to be defined in the SAP. Values outside the reference range will be flagged in the listings.

Vital sign variables (SBP, DBP, PR, respiration rate, and body temperature) and changes from Baseline (Day -1, or Day 1 before first treatment) will be summarized by time point and will be presented by treatment group.

The single 12-lead ECG will be recorded as timepoints defined in schedule of activities.

Descriptive statistics will be presented for ECG values and changes from Baseline (Day -1, before first treatment, Day 6, and Day 11) through treatment periods.

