4 POPULATIONS FOR ANALYSIS

Analysis Sets will be generated using the definitions in [Table 3](#)

Table 3 Definition of analysis sets

Population	Definition/Criteria	Randomized vs. Actual Treatment
ASPS	All Study Participants Set includes all study participants who signed the ICF.	ASPS will be analyzed as randomized. Non-randomized participants will be defined as “Screen Failures”
RS	Randomized Set includes all study participants who are randomized.	RS will be analyzed as randomized
SS	The Safety Set includes all study participants who are randomized and receive full or partial study medication. Study participants will be classified according to the treatment that the participants actually received. Participants who have data documenting they did not administer investigational intervention, even if received, are excluded from the SS.	SS will be analyzed according to the treatment actually received.
PKS	The Pharmacokinetic Set includes all participants of the SS, who received at least 1 total dose of study medication and have at least 1 observable PK measurement without important protocol deviations that would affect the PK. If a study participant in the PKS is missing individual time points or individual time points are otherwise non-evaluable, the study participant will be included in the PKS, but those individual time points will be identified as missing in listings.	PKS will be analyzed according to the treatment actually received.

Population	Definition/Criteria	Randomized vs. Actual Treatment
	All study participants in the PKS will be included in the listings and derivation of PK parameters. Note: some participants may have missing PK parameters if there are insufficient concentrations to derive them.	

ASPS=All Study Participants Set; ICF=Informed Consent Form; PK=pharmacokinetic(s); PKS=Pharmacokinetic Set; RS=Randomized Set; SS=Safety Set

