5.1.1.2 Protocol Deviations

Protocol deviations are specified in Appendix 1 (Section 6.1.2).

All protocol deviations will be reviewed at the Data Cleaning Meetings (DCM) and decisions made on whether they should be considered important or not.

Important protocol deviations (IPDs) are deviations from the protocol which could potentially have a meaningful impact on study conduct or on either the primary or key secondary outcome(s) for an individual study participant. The criteria for identifying such protocol deviations will be defined within the IPD specifications document.

Important protocol deviations will be categorized as follows:

1. Inclusion/exclusion criteria deviations
2. Incorrect treatment or dose administered
3. Procedural non-compliance
4. Prohibited concomitant medication use
5. Withdrawal criteria deviation

All IPDs will be reviewed as part of the ongoing data cleaning process and data evaluation. At least one Data Evaluation Meeting (DEM) will be performed prior to the final database lock after all data have been verified/coded/entered into the database to discuss exclusion of study participants from analysis populations.

Participants may be excluded from the safety set if they do not pass the inclusion/exclusion criteria. However, should a participant be mistakenly dosed despite failing the inclusion/exclusion criteria, then their safety data would need to be reported as part of the safety analysis. Participants may be excluded from other analysis sets, but this will be determined on a case-by-case basis. If the deviation is deemed to have the potential to bias the analyses for the duration of the study then the whole participant may be removed in a sensitivity analysis on the key endpoints. The removal of the participant and the rationale will be clearly documented within the relevant TFLs.

Important protocol deviations will be identified and classified by the deviation types in the IPD document. A listing of all IPDs identified at the DCMs will be presented for all participants based on the safety set and will include the deviation type and description.

The IPDs will be tabulated using the SS and will present the deviation type and description by treatment group.

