Adverse events will be assigned to Treatment Periods, based on the onset date/time of the AE. Assignment to Treatment Periods will be done after missing dates have been imputed as described above. AE will be assigned to a treatment based on the treatment received in the Treatment Periods as given in [Table 10](#).

Table 10 AE Treatment Period Assignment

Study	Period	Start	End
UP0152	Treatment Period 1	Start date is on or after administration of treatment in Treatment Period 1	Prior to administration of treatment in Treatment Period 2
	Treatment Period 2	Start date is on or after administration of treatment in Treatment Period 2	Prior to administration of treatment in Treatment Period 3
	Treatment Period 3	Start date is on or after administration of treatment in Treatment Period 3	

The following summaries will be provided by formulation and feeding condition groups:

- Incidence of TEAEs – Overview
- Incidence of TEAEs
- Incidence of Serious TEAEs
- Incidence of TEAEs leading to study discontinuation
- Incidence of TEAEs leading to permanent treatment discontinuation
- Incidence of TEAEs by maximum intensity
- Incidence of TEAEs by relationship to study medication

AEs will be presented as “number of participant (percentage of participant) [number of events]”. In this style of output, “[number of events]” will include all cases of an AE including repeat occurrences in individual participant, while “number of participant” will count each participant only once.

AEs will be presented by system organ class (SOC), high level term (HLT) and preferred term (PT) in a frequency table, giving the number of events, the number of participants, and the percentage of participants who experienced the event. Participants with multiple AEs are only counted once within each PT, each HLT and within each SOC.

Summaries by maximum severity will count each participant at most once within each MedDRA level based on the maximum severity/event intensity within that MedDRA level.

In summaries including intensity, the following intensity categories will be summarized: ‘Mild’, ‘Moderate’, ‘Severe’. Participants who experience the same event multiple times will be included in the most severe category for tabulations by maximum intensity. Events with missing intensity will be considered as ‘Severe’ events for summary purposes but recorded as missing in the listings.

All summaries will be sorted alphabetically by SOC. Within SOC, it will be sorted by decreasing frequency of PT.

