6.1.2 Protocol deviations

Important protocol deviations (IPDs) are deviations from the protocol that potentially could have a meaningful impact on study conduct, safety, or PK outcomes for an individual study participant. Furthermore, study participants will be excluded from the Safety Set only when there is documented evidence that they received no treatment. The criteria for identifying IPDs and the classification of IPDs will be defined within the Protocol Deviation Assessment Plan. IPDs will be reviewed as part of the Data Cleaning Meeting and Data Evaluation Meeting (DEM). Any important deviation will be identified and documented before unblinding to confirm exclusion from analysis sets.

Protocol deviations will be classified as follows:

- AE SAE
- Disallowed medications
- Inclusion/Exclusion criteria
- Informed Consent
- Study treatment
- Other
- Procedures/tests
- Procedures/tests/lab
- Visit schedule
- Withdrawal criteria
- Time window deviation

The IPDs will be tabulated using the SS by study parts and sequence, and will present the deviation type.

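### The SAP tabulates laboratory and vital sign data by sequence where the protocol asks for treatment group, names no shift-table variable, omits seven post-dose analytes from Table 11, and declares no change

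*SAP*

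**What the plan says.** **Grouping.** Protocol 9.2.4.1 says of laboratory variables, and again of vital signs, that values and changes from Baseline "will be summarized by time point and will be presented by treatment group". SAP 5.5.3.1.1 says: "Laboratory variables and changes from Baseline will be summarized using descriptive statistics by time point and sequence". SAP 5.5.3.2.1 uses the same grouping for vital signs, and SAP Table 7 gives time point and sequence for both.

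**Shift tables.** For laboratory values categorised by reference range, protocol 9.2.4.1 says that "shift tables from Baseline to each post-Baseline time point will be presented for selected variables to be defined in the SAP". The SAP text specifies no shift table and names no variable for one.

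**Analytes.** SAP 5.5.3.1 points to Table 11 for the protocol-required parameters and says that any others are listed but not tabulated.

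**Changes from protocol.** SAP 6.4 (Appendix 4) answers that none apply.

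**The concern.** In a 3-treatment, 6-sequence crossover, sequence and treatment are different groupings. Every participant in every sequence takes the capsule fasted (A), the tablet fasted (B) and the tablet fed (C). A sequence column therefore mixes all three as the time points advance. The secondary objective is safety and tolerability by formulation and feeding condition, and these tables do not show that directly.

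Two further gaps add to this. The protocol leaves the choice of shift-table variables to the SAP, and the SAP does not make it. Some analytes that the protocol requires may also never be tabulated, because Table 11 does not carry them. Since SAP 6.4 declares nothing, a reader of the study report would not know that the tables differ from those the protocol promised.

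**Working it through.** **1. What treatment group means here.** The protocol does not define the term, so its use has to settle the meaning.

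- Protocol 9.2.4 uses the same term for adverse events: "The occurrence and incidence of TEAEs will be summarized by MedDRA system organ class and preferred term and by treatment group".
- SAP 5.5.2 carries that out as formulation and feeding condition: "The following summaries will be provided by formulation and feeding condition groups".
- SAP Table 3 points the same way for the Safety Set: "SS will be analyzed according to the treatment actually received".
- Against this, the SAP uses the term loosely for important protocol deviations. Section 5.1.1.2 says "The IPDs will be tabulated using the SS and will present the deviation type and description by treatment group", while 6.1.2 says "The IPDs will be tabulated using the SS by study parts and sequence".

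The natural reading is A, B and C. The loose use shows that the SAP should define the term.

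**2. Where each treatment's values fall.** From the sequences in protocol Table 4-1:

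| | A | B | C |
|---|---|---|---|
| Period 1 | ABC, ACB | BCA, BAC | CAB, CBA |
| Period 2 | CAB, BAC | ABC, CBA | BCA, ACB |
| Period 3 | BCA, CBA | CAB, ACB | ABC, BAC |

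Each treatment occupies two of the six sequence columns, and a different pair after each period.

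**3. Cell sizes.** Protocol 4.1 gives 18 randomised and a minimum of 2 completers per sequence. Equal allocation is assumed, because neither document states it.

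- By sequence: 18/6 = 3 per cell (2 at the minimum).
- By treatment on one study day: 2 sequences × 3 = 6 (2 × 2 = 4 at the minimum).
- By treatment, pooling the three periods for the hepatic tests taken 96 h after each dose: 3 × 6 = 18.

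**4. Time after dose** (protocol 1.3 and its footnotes b, c and e).

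- Day 1 to 5, Day 6 to 10 and Day 11 to 15: 4 × 24 = 96 h.
- Day 1 to predose Day 6, and Day 6 to predose Day 11 (vital signs): 5 × 24 = 120 h.
- Safety follow-up, 5 to 9 days after the final dose: 120 to 216 h.

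Protocol 2.2 gives a half-life of about 11 to 13 h. The range is therefore 96/13 = 7.4 to 216/11 = 19.6 half-lives. By-treatment tables would also show only late values. Days 5 and 10 carry hepatic tests only, so full panels after dosing exist only on Day 15 and at follow-up.

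**5. Analytes.** Comparing protocol Table 10-1 with SAP Table 11:

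- Missing, and in panels scheduled after dosing: INR, PT, aPTT, creatine phosphokinase, lactate dehydrogenase, aldolase and albumin/creatinine ratio. That is 3 + 3 + 1 = 7.
- Missing, but scheduled only before dosing: eGFR, hepatitis B core antibody, total IgE, urine alcohol and cotinine. These 5 do not affect post-dose tables.

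If Table 11 is the full list of protocol-required parameters, the seven are listed only. If protocol-required means Table 10-1, they are tabulated. The SAP does not say which.

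**The case against.** **The term could mean sequence.** It is undefined, SAP 5.1.1.3 bases safety analyses on treatment as randomised by default, and randomisation is to a sequence. Table 7 separates adverse events from laboratory and vital sign data in a way that looks deliberate. This reading is weak. The same protocol term becomes formulation and feeding condition for adverse events, and 5.1.1.3 itself turns to the treatment actually received when the two differ. The ambiguity does stand as a reason to define the term.

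**Treatment columns would not isolate a treatment either.** Baseline precedes the first dose, and by Day 15 every completer has taken all three treatments. Only Day 5 hepatic tests and Day 6 predose vital signs follow a single treatment. This is true and limits what either layout can show. However, the protocol itself chose treatment-group display with a single pre-first-dose Baseline, so it does not excuse an undeclared change.

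**Nothing is lost.** Listings remain, time point plus sequence identifies the preceding treatment, and adverse events and the Potential Hy's Law listing are already by formulation and feeding condition. This stands and keeps the consequence modest. It still leaves the reader to rebuild the required table from column pairs that change each period.

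**Shift tables and analytes are less certain.** The SAP relies on standard table shells that are not in the documents, so a shift table may be planned there. Only the missing specification and variable names in the SAP are established. A footnote to protocol Table 10-1 also treats INR as conditional on being measured, although the table lists coagulation under clinical chemistry. That makes routine INR less clear-cut but does not explain the other omissions.

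**Conclusion.** The concern holds. The grouping departs from protocol 9.2.4.1 for laboratory and vital sign data, and SAP 6.4 is wrong to report no change. Table 11 is incomplete by seven analytes scheduled after dosing. The unnamed shift-table variables are missing detail rather than an error.

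The size is modest. Cells hold about 3 participants rather than 6 per treatment per study day, assuming equal allocation. The values are exploratory and come 7.4 or more half-lives after dose. No primary or secondary endpoint is affected. The conclusion rests on reading treatment group as A, B and C, which the SAP's own handling of adverse events supports. It should be corrected because the correction is simple and lets the tables address safety by formulation and feeding condition.

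**What to change.** - In SAP Table 7, 5.5.3.1.1 and 5.5.3.2.1, summarise laboratory and vital sign data by formulation and feeding condition and time point, and define treatment group that way. ECG appears in the same part of Table 7. The protocol sets no grouping for it, so state separately which grouping ECG keeps.
- Attribute each post-dose value to the most recent treatment received. Day 5 hepatic tests and Day 6 predose vital signs go to the Period 1 treatment, and Day 10 hepatic tests and Day 11 predose vital signs to the Period 2 treatment. Day 15 and follow-up values go to the Period 3 treatment, and early termination values to the last treatment received.
- State that this rule overrides SAP Table 4 for predose values on Days 6 and 11, because that table places those days in Treatment Periods 2 and 3.
- Note that full laboratory panels have no end-of-period value for Periods 1 and 2, and that later values follow more than one treatment.
- Name the shift-table variables and specify the tables.
- Complete Table 11 from protocol Table 10-1.
- Declare and justify in SAP 6.4 any departure that is kept.

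The cost is SAP wording and table shells. The Schedule of Activities already collects every value used, so no new assessment is needed.

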5.5.3.2 Vital Signs

Supine vital signs measured within UP0152 include:

- Pulse rate
- Systolic blood pressure
- Diastolic blood pressure
- Respiratory rate
- Body temperature

Vital signs will be measured in triplicate. The mean values will be calculated and recorded on the CRF.

Reference ranges for each vital sign will be recorded on the CRF. Clinically significant abnormalities will be flagged in the listings.

5.5.3.2.1 Vital Sign Values Over Time

The vital sign variables and changes from Baseline will be summarized using descriptive statistics by time point and sequence. A listing will be provided for the SS.

5.5.3.3 Electrocardiograms

The following ECG parameters will be obtained:

- Heart rate (beats/min),
- PR-interval (msec [milliseconds]),
- QRS-duration (msec),
- QT-interval (msec),
- QTcF (QT corrected for heart rate using Fridericia's formula) (msec),
- Investigator's conclusion on ECG profile.

5.5.3.3.1 ECG Values Over Time

The electrocardiogram results and changes from Baseline will be summarized using descriptive statistics by time point and sequence. A by-participant listing will be provided for the SS.

The following cut-points in QTcF based on the mean of the triplicate data will be summarized categorically (number and percentage of participants).

For observed data:

- <450 msec
- ≥ 450 to <480 msec
- ≥ 480 to <500 msec
- ≥ 500 msec

For change from Baseline in QTcF:

- <30 msec
- ≥ 30 to <60 msec
- ≥ 60 msec

5.5.3.4 Physical examination

A by-participant listing will be provided for physical examinations for the SS.

5.6 Subgroup analyses

Not Applicable.

5.7 Interim Analyses

No Interim Analysis is planned in this study.

5.8 Safety Monitoring Committee (SMC)

No Safety Monitoring Committee is planned in this study.

6 SUPPORTING DOCUMENTATION

6.1 Appendix 1 Non-key analysis specifications

6.1.1 Baseline characteristics and demographics

The body mass index (BMI) value collected in the eCRF will not be used for this summary. The BMI will be recalculated using the following formula and reported to 1 decimal place:

$$BMI(kg/m^2) = \frac{\text{body weight at screening (kg)}}{[\text{height at screening (m)}]^2} \quad (3)$$

6.1.2 Protocol deviations

Important protocol deviations (IPDs) are deviations from the protocol that potentially could have a meaningful impact on study conduct, safety, or PK outcomes for an individual study participant. Furthermore, study participants will be excluded from the Safety Set only when there is documented evidence that they received no treatment. The criteria for identifying IPDs and the classification of IPDs will be defined within the Protocol Deviation Assessment Plan. IPDs will be reviewed as part of the Data Cleaning Meeting and Data Evaluation Meeting (DEM). Any important deviation will be identified and documented before unblinding to confirm exclusion from analysis sets.

Protocol deviations will be classified as follows:

- AE SAE
- Disallowed medications
- Inclusion/Exclusion criteria
- Informed Consent
- Study treatment
- Other
- Procedures/tests
- Procedures/tests/lab
- Visit schedule
- Withdrawal criteria
- Time window deviation

The IPDs will be tabulated using the SS by study parts and sequence, and will present the deviation type.

